6.3.2. Additional considerations

The immunogenicity summaries will be generated on the adapted ATP cohort for immunogenicity.

For anti-PRP, the percentage of subjects with antibody concentrations $\geq 1.0 \mu\text{g/ml}$ will also be presented with exact 95% CI.

6.4. Analysis of safety**6.4.1. Analysis of safety planned in the protocol**

Analysis of safety relative to the primary epoch will include analysis of safety data collected following administration of the three primary doses of study vaccine. Analysis of safety relative to the booster epoch will include analysis of safety data collected following administration of the booster dose of study vaccine. At this second stage, in order to avoid missing SAEs that have been reported, an SAE summary table including all the events reported during the entire study period will also be generated.

The analysis will be based on the Total vaccinated cohort for both primary and booster epochs. All analyses are descriptive.

- The overall percentage of subjects/doses with at least one local symptom (solicited or unsolicited), with at least one general symptom (solicited or unsolicited) and with any symptom (solicited or unsolicited) during the 4-day (Days 0-3) solicited follow-up period will be tabulated with exact 95% CI after each vaccine dose and overall primary doses. The same calculations will be done for symptoms (solicited or unsolicited) rated as grade 3 in intensity, for symptoms (solicited or unsolicited) leading to medical advice and for symptoms (solicited or unsolicited) assessed as causally related to vaccination.
- The overall percentage of subjects/doses and of subjects reporting each individual solicited local and general symptom during the 4-day (Days 0-3) solicited follow-up period will be tabulated after each vaccine dose and overall primary doses, with exact 95% CI after each vaccine dose and overall primary doses. The same calculations will be done for each individual solicited symptom rated as grade 3 in intensity and for each individual solicited symptom assessed as causally related to vaccination.
- Occurrence of fever will be reported per 0.5°C cumulative increments.

- The verbatim reports of unsolicited AEs will be reviewed by a physician and the signs and symptoms will be coded according to MedDRA. Every verbatim term will be matched with the appropriate Preferred Term. The percentage of subjects with unsolicited AEs occurring within 31-day (Days 0-30) follow-up period after any dose (after primary or booster vaccination) with its exact 95% CI will be tabulated by preferred term. Similar tabulation will be done for unsolicited AEs rated as grade 3, for unsolicited AEs with causal relationship to vaccination and AE(s)/SAE(s) leading to withdrawal from the study.
- The percentage of subjects who receive at least one concomitant medication during the 4-day (Days 0-3) solicited follow-up period and during the entire primary/booster epoch will be tabulated (with exact 95% CI after each vaccine dose and overall).
- Any large injection site reaction (defined as a swelling with a diameter > 50 mm, noticeable diffuse swelling or noticeable increase in limb circumference) after booster vaccination will be described in detail.

SAE(s) will be described in detail.

Handling of missing data:

- For a given subject and the analysis of solicited symptoms four days post-vaccination, missing or non-evaluable measurements will not be replaced. Therefore the analysis of the solicited symptoms based on the TVC will include only vaccinated subjects and doses with documented safety data (i.e., symptom screen completed).
- For analysis of unsolicited AEs, such as SAEs or AEs by primary Medical Dictionary for Regulatory Activities (MedDRA) term, and for the analysis of concomitant medications, all vaccinated subjects will be considered. Subjects, who do not report the event or the concomitant medication, will be considered as subjects without the event or the concomitant medication, respectively.
- For summaries reporting both solicited symptoms and unsolicited AEs, all vaccinated subjects will be considered. Subjects, who do not report the event or the concomitant medication, will be considered as subjects without the event or the concomitant medication, respectively.

6.4.2. Additional considerations

The summary of each solicited symptom and unsolicited adverse event will also be done for medically attended symptom/adverse event and for grade 3 causally related.

The percentage of subjects who receive concomitant medication and antipyretic medication during the entire study period will be tabulated for the 31-day (Day 0-30) follow-up period since this is the period planned for collecting concomitant medications.

7. ANALYSIS INTERPRETATION

All analyses will be conducted in a descriptive manner.

8. CONDUCT OF ANALYSES

Any deviation(s) or change(s) from the original statistical plan outlined in this protocol will be described and justified in the final study report.

8.1. Sequence of analyses

The analyses will be performed stepwise:

- A final analysis of the primary epoch will be conducted on all immunogenicity and safety data obtained up to one month after administration of the third primary dose of study vaccine (Visit 4), as soon as the data will be as clean as possible. This will include the analysis of the primary immunogenicity objectives related to the primary epoch and analysis of solicited symptoms and unsolicited adverse events reported within the 4-day (Days 0-3) period and 31-day (Days 0-30) period following the primary vaccination, respectively, and the SAEs reported during the primary epoch.
- Analysis of the booster epoch will be conducted on all cleaned immunogenicity and safety data obtained up to one month after administration of the booster dose of study vaccine (Visit 6). This will include analysis of the secondary immunogenicity objectives related to the booster epoch and analysis of solicited symptoms and unsolicited adverse events reported within the 4-day (Days 0-3) period and 31-day (Days 0-30) period following administration of the booster dose of study vaccine, respectively, and the SAEs reported during the booster epoch. At this second stage, in order to avoid missing SAEs that have been reported, an SAE summary table including all the events reported during the entire study period will also be generated.

8.2. Statistical considerations for interim analyses

All analyses will be conducted on final data and therefore no statistical adjustment for interim analyses is required.

Description	Analysis ID	Disclosure Purpose (IN=internal, CTRS=public posting, SR=study report and public posting)	Dry run review needed (Y/N)	Study Headline Summary (SHS)requiring expedited communication to upper management (Yes/No)	Reference for TFL
Primary Epoch Analysis	E1_01	CTRS	Yes	No	TFL TOC
Final Analysis	E1_02	SR and CTRS	Yes	Yes	TFL TOC

8.3. Statistical considerations for interim analyses

The study is descriptive and the interim analysis will be performed on final/clean data. Therefore there is no adjustment for multiplicity resulting from the interim analysis.

9. CHANGES FROM PLANNED ANALYSES

Reference to ATP cohort for safety was removed in the description of the ATP cohort for immunogenicity as the ATP cohort for safety was not defined

The Total vaccinated cohort for the booster epoch was defined section [5.1.1](#)

Note that the 2 first secondary endpoints described in the protocol:synopsis refer erroneously to results one month after the Third dose of the primary vaccination as opposed to the secondary endpoints described in the body of the protocol which refer one month post-booster vaccination.

10. LIST OF FINAL REPORT TABLES, LISTINGS AND FIGURES

The TFL TOC provides the list of tables/listings and figures needed for the study report. It also identifies the tables eligible for each analyses and their role (synopsis, in-text, post-text, SHS, CTRS,...). Note that all TFL aimed to be included as post-text are noted as post-text even if these are tabulation of individual data such as listing of SAE. The post-text material contain all source material for the study report and accordingly a post-text table may be redundant with an in-text table.

The mock tables referred under column named 'layout' can be found in Section 13 of this SAP.

The following group name will be used in the TFLs, to be in line with the T-domains:

Group order in tables	Group label in tables	Group definition for footnote
1	DTPa-IPV/Hib	DTPa-IPV/Hib at 3, 4.5, 6 and 18 months of age

11. ANNEX 1 STANDARD DATA DERIVATION RULE AND STATISTICAL METHODS

11.1. Statistical Method References

The exact two-sided 95% CIs for a proportion within a group will be the Clopper-Pearson exact CI [Clopper CJ, Pearson ES. The use of confidence or fiducial limits illustrated in the case of binomial. *Biometrika*. 1934;26:404-413].

11.2. Standard data derivation

11.2.1. Date derivation

- SAS date derived from a character date: in case day is missing, 15 is used. In case day & month are missing, 30June is used.
- Onset day for an event (ae, medication, vaccination, ...): the onset day is the number of days between the last study vaccination & the onset/start date of the event. This is 0 for an event starting on the same day as a vaccination. See SAS date derived in case the start date of the event is incomplete.

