8.2. Detecting and recording adverse events and serious adverse events

8.2.1. Time period for detecting and recording adverse events and serious adverse events

All AEs starting following administration of each dose of study vaccine (Day 0 to Day 30) must be recorded into the appropriate section of the eCRF, irrespective of intensity or whether or not they are considered vaccination-related.

The time period for collecting and recording SAEs will begin at the first receipt of study vaccine and will end 30 days following administration of the last dose of study vaccine for each subject. See Section 8.3 for instructions on reporting of SAEs.

All AEs/SAEs leading to withdrawal from the study will be collected and recorded from the time of the first receipt of study vaccine.

SAEs that are related to the investigational vaccine will be collected and recorded from the time of the first receipt of study vaccine until the subject is discharged from the study.

In addition to the above-mentioned reporting requirements and in order to fulfil international reporting obligations, SAEs that are related to study participation (i.e. protocol-mandated procedures, invasive tests, a change from existing therapy) or are related to a concurrent GSK medication/vaccine will be collected and recorded from the time the subject's parent/*adoptive parent* consents to participate in the study until she/he is discharged from the study.

An overview of the protocol-required reporting periods for AEs and SAEs is given in Table 13.

(Amended 11 October 2016)

Table 13 Reporting periods for adverse events and serious adverse events

Event	Pre-V1*	V1	3 d post-V1	30 d post-V1	V2	3 d post-V2	30 d post-V2	V3	3 d post-V3	30 d post-V3	V4	B	3 d post B	30 d post-B	(Study Conclusion)
Time-point		D0			M1.5			M3			M4	M15			M16
Age of subject	3m	3m			4.5m			6m			7m	18m			19m
Study Visit	Visit 1	Visit 1			Visit 2			Visit 3			Visit 4	Visit 5			Visit 6
Solicited local and general AEs															
Large injection site reactions															
Unsolicited AEs															
AEs/SAEs leading to withdrawal from the study															
SAEs related to the investigational vaccine															
SAEs related to study participation or concurrent GSK medication/vaccine															

* i.e. consent obtained. Pre-V: pre-vaccination; V: vaccination; Post-V: post-vaccination; B: Booster vaccination; d: days; D: Day; m: months; M: Month

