11.2.2. Dose number

- The study dose number is defined in reference to the number of study visits at which vaccination occurred. More specifically dose 1 refers to all vaccines administered at the first vaccination visit while dose 2 corresponds to all vaccinations administered at the second vaccination visit even if this is the first time a product is administered to the subject.
- Relative dose: the relative dose for an event (AE, medication, vaccination) is the most recent study dose given before an event. In case the event takes place on the day a study dose is given, the related dose will be that of the study dose, even if the event actually took place before vaccination. For instance, if an adverse event begins on the day of the study vaccination but prior to administration of the vaccine, it will be assigned to this dose. In case a study dose is not administered and an event occurs after the subsequent study dose (eg 3rd study dose), the relative dose of the event will be study dose associated to the subsequent study dose (eg dose 3).
- The number of doses for a product is the number of time the product was administered to a subject.
- The incidence per dose is the number of vaccination visits at which an event was reported among all vaccination visits.

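### A missing onset day is set to the 15th with no check against the dose date, so about a quarter to a third of post-dose adverse events with that gap would leave their own 31-day window

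*SAP*

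**What the plan says.** SAP 11.2.1 (Date derivation) gives two completion rules: "in case day is missing, 15 is used", and "In case day & month are missing, 30June is used". The next bullet defines timing: "the onset day is the number of days between the last study vaccination & the onset/start date of the event". It sends incomplete start dates back to the completion rules: "See SAS date derived in case the start date of the event is incomplete".

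SAP 11.2.2 (Dose number) then attributes the event: "the relative dose for an event (AE, medication, vaccination) is the most recent study dose given before an event". Its only nearby safeguard covers an event on the same calendar day as a dose, which goes to that dose.

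SAP 6.4.1 (Analysis of safety) tabulates by window: "The percentage of subjects with unsolicited AEs occurring within 31-day (Days 0-30) follow-up period after any dose".

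Protocol 8.2.1 sets what is collected: "All AEs starting following administration of each dose of study vaccine (Day 0 to Day 30) must be recorded". Under Protocol 5.6.15 a diary card is issued at each vaccination visit.

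**The concern.** An event on a post-dose diary card is already known to have followed that dose. The completion rule ignores this.

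- **Moved before the dose.** Dose on the 20th, onset recorded only as that month. Onset becomes the 15th, five days before vaccination. After Dose 1 there is no earlier vaccination from which to count, so the onset day is undefined. After Dose 2, given 45 days after Dose 1, the event becomes Day 40 of Dose 1 and is in neither window.
- **Moved past Day 30.** Dose on 10 March, true onset 2 April (Day 23), day not recorded. Onset becomes 15 April, which is Day 36.

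Such events would drop out of the 31-day unsolicited tables or be credited to the wrong dose. The loss is greatest for early onsets, where a vaccine effect is most plausible. The study has no control group to share the error.

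**Working it through.** The documents state no misclassification rate, so there is no figure to reproduce. The rule was applied directly.

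**Inputs from the documents.** Completion to the 15th or 30 June (SAP 11.2.1); attribution to the most recent dose (SAP 11.2.2); window Days 0-30 (SAP 6.4.1); gap between primary doses 45 days optimal, 28-62 allowed (Protocol Table 5).

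**Assumptions not in the documents.** Dose dates spread evenly over the calendar; the distribution of true onset over Days 0-30.

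**Formula.** For dose date d and true onset d + k (k = 0 to 30), let m be the 15th of the month containing d + k. The event leaves its own window if m - d < 0 or m - d > 30. All dose dates in four calendar years were enumerated.

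| Assumed onset | Before dose | After Day 30 | Leaves own window |
|---|---|---|---|
| Uniform, Days 0-30 | 13.5% | 11.1% | 24.6% |
| Linearly declining | 22.0% | 3.7% | 25.8% |
| Exponential, mean 10 days | 27.4% | 2.8% | 30.2% |
| Exponential, mean 7 days | 32.1% | 1.3% | 33.4% |
| Exponential, mean 5 days | 36.6% | 0.5% | 37.1% |
| All on Days 15-30 | 0.1% | 21.6% | 21.7% |
| All on Day 0 | 50.7% | 0% | 50.7% |

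(Entries are rounded separately.)

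**Hand checks.**
- Onset on Day 0 is moved whenever the dose falls after the 15th. That is 16 days in seven months, 15 in four and 13.25 on average in February: (7×16 + 4×15 + 13.25)/365.25 = 185.25/365.25 = 50.7%.
- Dose on the 16th, uniform onset: every onset in the dose month is moved to Day -1, and every onset in the next month stays inside. The same count over 12×31 gives 185.25/372 = 49.8%. A dose on the 1st gives only 1.8%.

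**Where the moved events go.** An event placed before its dose lands 1 to 16 days early. At 45-day spacing that is Day 45 - 16 = 29 to Day 45 - 1 = 44 after the previous dose. Only doses on the 30th or 31st put it back inside the previous window: 0.2% (uniform) or 0.9% (mean 7 days). So 24.6 - 0.2 = 24.4% and 33.4 - 0.9 = 32.5% of Dose 2 events fall in no window. In simulation of all four doses with primary gaps spread over 28-62 days, 21.7% and 28.8% are lost from every window, because more land in the previous dose's window.

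**Day and month missing.** With uniform dates, 30 June falls before the dose for 46.3% and after Day 30 for 45.2%, about 92% outside.

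**Medications.** These are recorded continuously to Day 30 after the booster (Protocol 6.7.1), so genuine out-of-window starts exist. With doses at Days 0, 45, 90 and 455 and starts uniform over the study, completing to the 15th moves 6.3% out of a 31-day window and 4.7% in. Over Days 0-120 the figures are 18.8% and 12.5%.

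**The case against.** The best reply is about reach. The percentages are shares of day-missing records, and the protocol works against such records. Parents fill in diary cards, site staff verify them in discussion at Visits 2, 3, 4 and 6 and chase unreturned ones (Protocol 5.6.15). Omissions in the eCRF are queried and entries checked against source (Protocol 11.1, 11.2). Analyses run on cleaned data (SAP 8.1). This stands: few partial dates are likely, and the effect on any reported percentage cannot be calculated.

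The key safety outputs are also largely protected. The SAE summary in SAP 6.4.1 covers the entire study without a post-dose window, SAEs are described individually, and solicited symptoms are graded from daily recordings (SAP 11.2.5). The study is descriptive, with no decision rule. This stands too.

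A reader might infer that the error always reduces counts. For non-serious unsolicited events, collected only on Days 0-30, it can only remove them or shift them to another dose. For medications it cannot be called one-sided: the outward and inward movements partly offset. Nor is every displaced event lost. With short gaps, some enter the previous dose's window and still count in the after-any-dose table.

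Finally, the SAP does not say how a completed date before Dose 1 is handled. Treating it as a pre-vaccination event is the natural reading, but an inference.

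None of this supplies the missing check. Followed literally, the rule can place an event known to be post-dose before its dose.

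**Conclusion.** Wrong as written, low priority. Among unsolicited adverse events that began on Days 0-30 after a dose and lack only the day, about 25% (uniform onset) to 33% (exponential, mean 7 days) would leave their own window. The more extreme onset patterns tried run from about 22% to 51%. At the planned 45-day spacing nearly all of the displaced events fall in no window or precede any vaccination. These figures rest on evenly spread dose dates and assumed onset patterns.

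It is tempting to conclude that a quarter to a third of adverse events, or serious events, would go unreported. The documents do not support that: the number of partial dates is not given, and the whole-study SAE table does not depend on the window.

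**What to change.** Amend SAP 11.2.1 as follows.

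- **Adverse event reported as post-dose, day missing.** Keep the 15th, but not earlier than the later of the dose date and the 1st of the recorded month, and not later than the earliest of Day 30, the month end and any recorded end date.
- **Day and month missing.** Replace 30 June with a date inside the same dose-date, Day 30 and end-date bounds, and state how it is chosen. Merely truncating 30 June to those bounds would put about 46% of events on Day 0 and 45% on Day 30.
- **Medications.** Bound only by the recorded month, the end date and any recorded before/after-dose information.
- **Source of the dose.** State that the dose comes from the diary card or visit under which the event was reported. SAP 11.2.2 at present attributes by date alone.

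The day-missing rule leaves 0% outside every 31-day window. About 0.5% still change dose, where the next dose came within 30 days.

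Moving every such event to the dose date, or to the 1st if the month is later, is simpler but worse. It puts 51% (uniform) to 80% (mean 7 days) on Day 0, and so 60% against a true 13%, or 87% against 44%, in Days 0-3, a period that SAP 6.4.1 also tabulates for unsolicited symptoms. The bounded 15th gives 21% and 44%.

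The cost is a short SAP amendment and a few lines of code. The exact day inside the window stays approximate, which slightly affects the Days 0-3 tables.

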11.2.2. Dose number

- The study dose number is defined in reference to the number of study visits at which vaccination occurred. More specifically dose 1 refers to all vaccines administered at the first vaccination visit while dose 2 corresponds to all vaccinations administered at the second vaccination visit even if this is the first time a product is administered to the subject.
- Relative dose: the relative dose for an event (AE, medication, vaccination) is the most recent study dose given before an event. In case the event takes place on the day a study dose is given, the related dose will be that of the study dose, even if the event actually took place before vaccination. For instance, if an adverse event begins on the day of the study vaccination but prior to administration of the vaccine, it will be assigned to this dose. In case a study dose is not administered and an event occurs after the subsequent study dose (eg 3rd study dose), the relative dose of the event will be study dose associated to the subsequent study dose (eg dose 3).
- The number of doses for a product is the number of time the product was administered to a subject.
- The incidence per dose is the number of vaccination visits at which an event was reported among all vaccination visits.

11.2.3. Demography

Age: Age at the reference activity, computed as the number of complete weeks between the date of birth and the reference activity.

Conversion of weight to kg: the following conversion rule is used:

Weight in Kilogram= weight in Pounds / 2.2 + weight in ounces / 35.2

The result is rounded to 2 decimals.

Conversion of height to cm: the following conversion rule is used:

Height in Centimetres = Height in Feet * 30.48+

Height in Inch * 2.54

The result is rounded to the unit (ie no decimal).

Conversion of temperature to °C: the following conversion rule is used:

Temperature in °Celsius = ((Temperature in °Fahrenheit -32) *5)/9

The result is rounded to 1 decimal.

11.2.4. Immunogenicity

- A seronegative subject is a subject whose antibody concentration/titre is below the assay cut-off.
- A seropositive subject is a subject whose antibody concentration/titre is greater than or equal to the assay cut-off.
- A seroprotected subject is a subject whose antibody concentration/titre is greater than or equal to the level defining clinical protection. The following seroprotection thresholds are applicable:
 - Anti-diphtheria antibody concentrations ≥ 0.1 IU/ml.
 - Anti-tetanus antibody concentrations ≥ 0.1 IU/ml.
 - Anti-poliovirus types 1, 2 and 3 antibody titres ≥ 8 .
 - Anti-PRP antibody concentrations ≥ 0.15 μ g/ml.
- The geometric mean titres (GMTs)/geometric mean concentrations (GMCs) calculations will be performed by taking the anti-log of the mean of the log₁₀ titre/concentration transformations. Antibody titres/concentrations below the cut-off of the assay will be given an arbitrary value of half the cut-off for the purpose of GMT/GMC calculation.
- In general, the assay cut-off is the value under which there is no quantifiable result available. For an assay with a specific ‘assay cut_off’ , numerical immuno result is derived from a character field (rawres):
 - If rawres is ‘NEG’ or ‘-’ or ‘(-)’, numeric result= assay cut_off/2,
 - if rawres is ‘POS’ or ‘+’ or ‘(+)’, numeric result = assay cut_off,
 - if rawres is ‘< value’ and value \leq assay cut_off, numeric result =assay cut_off/2,
 - if rawres is ‘< value’ and value $>$ assay cut_off, numeric result =value,
 - if rawres is ‘> value’ and value $<$ assay cut_off, numeric result =assay cut_off/2,
 - if rawres is ‘> value’ and value \geq assay cut_off, numeric result =value,
 - if rawres is ‘ \leq value’ or ‘ \geq value’ and value $<$ assay cut_off, numeric result =assay cut_off/2,
 - if rawres is ‘ \leq value’ or ‘ \geq value’ and value \geq assay cut_off, numeric result =value,
 - if rawres is a value $<$ assay cut_off, numeric result = assay cut_off/2,
 - if rawres is a value \geq assay cut_off, numeric result = rawres,
 - else numeric result is left blank.

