5.7.5. Immunological correlates of protection

For the following antigens in the DTPa-IPV/Hib vaccine, an immunological correlate of protection has been established:

- Specific antibodies against diphtheria toxoid (anti-diphtheria) and tetanus toxoid (anti-tetanus) will be measured by ELISA. The assay cut-off of ELISA is set at 0.1 International Units per ml (IU/ml), which provides a conservative estimate of the percentage of subjects deemed to be protected [Melville-Smith, 1983; Camargo, 1984].
- Data from subjects given unconjugated Hib vaccine suggest that, in the absence of induction of immunological memory, a concentration of 0.15 µg/ml is indicative of short-term protection, with 1 µg/ml considered indicative of long-term protection [Käyhty, 1983; Anderson, 1984].
- Antibodies against poliovirus types 1, 2 and 3 will be determined by a virus micro-neutralisation test adapted from the W H O Guidelines for WHO/EPI Collaborative Studies on Poliomyelitis [WHO, 1993]. Titres will be expressed in terms of the reciprocal of the dilution resulting in 50% inhibition. Samples with a titre greater than or equal to 1:8 will be considered as sero-positive and protective.
- No serological correlate of protection against pertussis has been established [Granström, 1987; Karpinsky, 1987]. Antibodies against the pertussis components pertussis toxoid (PT), filamentous haemagglutinin (FHA) and pertactin (PRN) will be measured by ELISA. The seropositivity cut-off for all three pertussis antibodies in ELISA is 5 EL.U/ml. Subjects with antibody concentration below the cut-off will be considered seronegative.

Assessment of the protection level will be done at least 4 weeks after completing the primary vaccination course and at least 4 weeks after the administration of the booster dose.

The immunological assay results will be communicated to the investigator as soon as they become available.

The investigator is encouraged to share the immunological assay results for non-responders with the study subject's parent(s)/*adoptive parent(s)*.

For the subjects identified as non-responders, it remains the responsibility of the investigator in charge of the subject's clinical management to determine the medical need for re-vaccination and to re-vaccinate the subjects as per local/regional practices.

(Amended 11 October 2016)

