1. DOCUMENT HISTORY

Date	Description	Protocol Version
16-FEB-2015	first version	Protocol 24-March-2014
10-AUG-2017	Amendment 1	Protocol Amendment 1 dated 11 October 2016
14-DEC-2017	Amendment 2	Protocol Amendment 1 dated 11 October 2016

The SAP amendment 1 was prepared in order to

1. Account for the new assay cut-off: During the course of the study, the assays used to measure the anti-D, -T, -PT, -FHA and -PRN IgG concentrations were re-developed and re-validated and both assay units and assay cut-offs were adapted. The new ELISAs for PT, FHA and PRN were calibrated against the WHO International Standard (NIBSC 06/140). This allowed the expression of concentrations measured with the new ELISAs in international units per milliliter (IU/mL) instead of the formerly used ELISA units per milliliter (ELU/mL). The newly validated DTPa ELISA's have a lower assay cut-off as compared to the one described in the protocol. The current assay cut-off is 0.057 IU/ml for anti-D, 0.043 IU/ml for anti-T, 2.693 IU/ml for anti-PT, 2.046 IU/ml for anti-FHA and 2.187 IU/ml for anti-PRN. An agreement between the old and new ELISAs was shown with regards to the two thresholds of clinical relevance for the DI/TE response (0.1 IU/mL and 1.0 IU/mL) and therefore the clinical endpoints and anti-D and anti-T are unchanged. In the absence of a correlate of protection for the pertussis antigens, the anti- PT, anti-FHA and anti-PRN antibody seropositivity endpoints were redefined based on the new assay cut-off.
2. Use the SAP template effective since 14-April-2017
3. Reflect the protocol amendment 1

The SAP amendment 2 was prepared in order to include the interim analysis of the primary vaccination epoch in the sequence of analysis and in order to reflect the way important protocol deviation will be summarised (Important protocol deviation not leading to elimination will be described using narrative instead of summary table).

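### The SAP's rule for 'less than' assay results would count an anti-D or anti-T result of '<0.1' IU/ml as seroprotected, if the laboratory ever reports one (minor)

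*SAP*

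**What the plan says.** SAP 11.2.4 derives each numeric result from a character field. A 'less than' result with a bound at or below the assay cut-off becomes half the cut-off. With a bound above the cut-off, the text reads "and value $>$ assay cut_off, numeric result =value".

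The same section defines responders inclusively: "A seroprotected subject is a subject whose antibody concentration/titre is greater than or equal to the level defining clinical protection". The first threshold listed is "Anti-diphtheria antibody concentrations ≥ 0.1 IU/ml". Tetanus has the same threshold, polio has 8, and anti-PRP has 0.15 µg/ml.

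The cut-offs changed during the study. Protocol 5.7.3 (Table 7) and 5.7.5 give 0.1 IU/ml for the anti-D and anti-T ELISAs. SAP section 1, describing Amendment 1, says: "The current assay cut-off is 0.057 IU/ml for anti-D, 0.043 IU/ml for anti-T". It leaves the anti-D and anti-T clinical endpoints unchanged.

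SAP 6.3.2 adds one summary: "For anti-PRP, the percentage of subjects with antibody concentrations" of at least 1.0 µg/ml.

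On what the laboratory can quantify, SAP 11.2.4 says: "In general, the assay cut-off is the value under which there is no quantifiable result available".

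**The concern.** A result reported as below 0.1 cannot also be 0.1 or more. The rule gives it the value 0.1, and the inclusive threshold then counts it as a responder. No other section overrides the rule or says that responder status is read from the raw field.

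While cut-off and threshold were both 0.1 IU/ml, this could not happen at exactly 0.1, because a `<0.1` was halved to 0.05. The new cut-offs lie below the threshold, and the rule refers only to the cut-off.

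Anti-D and anti-T seroprotection are primary endpoints (SAP 4.1) and are repeated after the booster (SAP 4.2). If such a result occurred, the reported rate would move in the favourable direction, and an upper bound would enter the GMC as though it had been measured.

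**Working it through.** **Inputs.** The rule and thresholds are from SAP 11.2.4. The current cut-offs for anti-D, anti-T, PT, FHA and PRN are from SAP section 1. The cut-offs for PRP (0.15) and polio (8), and the former anti-D and anti-T cut-off (0.1), are from Protocol Table 7. The target of 200 evaluable children is from Protocol 10.3.

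**Step 1: apply the rule.** For a raw `<v` and cut-off c, the result is c/2 if v ≤ c, and v if v > c. The result is then compared with the threshold by ≥. The raw strings are hypothetical.

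| Assay (cut-off) | Raw result | Number assigned | Compared with | Counted as | Agrees with raw result? |
|---|---|---|---|---|---|
| Anti-D or anti-T, protocol (0.1) | `<0.1` | 0.05 | 0.1 | not protected | yes |
| Anti-D (0.057) | `<0.057` | 0.0285 | 0.1 | not protected | yes |
| Anti-D (0.057) | `<0.08` | 0.08 | 0.1 | not protected | yes |
| Anti-D (0.057) | `<0.1` | 0.1 | 0.1 | protected | **no** |
| Anti-T (0.043) | `<0.043` | 0.0215 | 0.1 | not protected | yes |
| Anti-T (0.043) | `<0.1` | 0.1 | 0.1 | protected | **no** |
| Anti-D or anti-T (current) | `<0.2` | 0.2 | 0.1 | protected | cannot be told |
| PRP (0.15) | `<0.15` | 0.075 | 0.15 | not protected | yes |
| PRP (0.15) | `<0.3` | 0.3 | 0.15 | protected | cannot be told |
| PRP (0.15) | `<1.0` | 1.0 | 1.0 | at or above 1.0 | **no** |
| Polio (8) | `<8` | 4 | 8 | not protected | yes |
| Polio (8) | `<16` | 16 | 8 | protected | cannot be told |
| PT (2.693), FHA (2.046), PRN (2.187) | `<5` | 5 | cut-off | seropositive | cannot be told |

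A certain error needs a bound that is above the cut-off and equal to the threshold. Bounds above the threshold are indeterminate, and the rule counts them all as responders.

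**Step 2: effect on a rate.** Exact (Clopper-Pearson) intervals reproduce all nine rows of Protocol Table 16. For example, 190/200 = 95% gives 91.0 to 97.6. For 200/200 the lower limit is 0.025^(1/200) = 0.982, the table's 98.2.

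One misclassified child adds 1/200 = 0.5 percentage points. Suppose one child has anti-D `<0.1` and the other 199 are protected:

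- correct: 199/200 = 99.5% (97.2 to 100.0)
- as derived: 200/200 = 100% (98.2 to 100)

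**Step 3: effect on the GMC.** Entering 0.1 in place of a lower value x for one child in 200 multiplies the GMC by (0.1/x)^(1/200).

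- x just under 0.1: the ratio is close to 1. At x = 0.09 it is (0.1/0.09)^(1/200) = 1.0005, or +0.05%.
- x = half the cut-off, the lowest value that the SAP itself would enter: for anti-D, (0.1/0.0285)^(1/200) = 1.0063, or +0.6%; for anti-T, (0.1/0.0215)^(1/200) = 1.0077, or +0.8%.

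**The case against.** The strongest reply is that the input may never arise. If the cut-off is the limit below which nothing can be quantified, a concentration between 0.057 (or 0.043) and 0.1 is reported as a number, and anything lower is reported as below the cut-off, which the rule handles correctly. Lowering the cut-off also removed the natural source of `<0.1`, since 0.1 was the old assay's limit. The rule works with each assay's own cut-off, so an old-assay `<0.1` would still be halved to 0.05. An error needs a new-assay sample reported with a bound of 0.1. All of this stands, and it limits the practical weight of the point.

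It is also fair that SAP section 6 presents this annex as standard derivation rules. The list covers many kinds of string, and naming one does not mean that the study will use it. Nor does every branch favour the vaccine: a 'greater than' result with a bound below the cut-off is set to half the cut-off.

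What does not fall away is the logic. The SAP names this input, and for a bound equal to the threshold its answer contradicts the result. That a branch is generic or rarely used is a reason to delete or correct it cheaply.

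**Conclusion.** The rule is wrong as written for one narrow kind of input: a 'less than' result whose bound is above the cut-off and equal to the threshold. That means `<0.1` for anti-D and anti-T, and `<1.0` for anti-PRP in the added summary. Each such result overstates the rate by 0.5 points at n = 200. It overstates the GMC by between about zero and 0.6% (anti-D) or 0.8% (anti-T). The number of such results is not documented and may be zero, in which case nothing changes. All analyses are descriptive (SAP 6.3.1 and 7), so no pass/fail decision depends on it. The point is minor.

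A reader might infer three stronger things that the documents do not support:

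- **That the new cut-offs have led to children being misclassified.** No such laboratory result is shown.
- **That every bound above a threshold is an error.** An anti-D `<0.2` may be above or below 0.1. Counting it as a responder is unjustified, but it is not known to be false.
- **That the PRP, polio and pertussis examples follow from the lower cut-offs.** For PRP and polio the documents show no change of cut-off. For pertussis a `<5` is indeterminate, not a certain error.

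**What to change.** First ask the laboratory whether any result above the cut-off can be issued as a 'less than' value. If it confirms that all are reported as numbers, delete the branch from SAP 11.2.4; nothing more is needed.

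Otherwise amend that line as follows:

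- **Bound at or below a threshold:** classify the result as below that threshold, from the raw result and not from the number used for the GMC.
- **Bound above a threshold:** treat the result as indeterminate and report the count per antigen and visit. If any occur, show the rate twice: with them counted as non-responders, and with them excluded as non-evaluable. The second matches the missing-data rule in SAP 6.3.1.
- **GMC:** do not enter the upper bound as a measured value. Show the GMC with and without such results. For the version that includes them, state the value used; no particular substitute is prescribed here.

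The cost is a few lines of SAP text and derivation code, plus one extra display if such results exist. No sample needs re-testing and no child is lost from the primary presentation.
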